8.9 Definition of End of Trial

The end of trial is the date of the last visit of the last participant.

8.10 Discontinuation/Withdrawal of Participants from Study Treatment

Each participant has the right to withdraw from the study at any time without needing to give a reason. In addition, the Investigator may discontinue a participant from the study at any time if the Investigator considers it necessary for any reason including:-

- Participant intolerance to study medication, as assessed at each visit by the study team, will necessitate withdrawal of participant from the study as study drug dose will not be reduced during the trial
- Ineligibility (either arising during the study or retrospective having been overlooked at screening)
- Significant protocol deviation
- Significant non-compliance with treatment regimen or study requirements
- An adverse event which requires discontinuation of the study medication or results in inability to continue to comply with study procedures
- Disease progression which requires discontinuation of the study medication or results in inability to continue to comply with study procedures
- Consent withdrawn
- Lost to follow up

The reason for withdrawal will be recorded in the CRF and medical records if known. If the participant is withdrawn due to an adverse event, the investigator will arrange for safety follow-up visits or telephone calls until the adverse event has resolved or stabilised. The duration of safety follow-ups will be at least five half-lives of the study medication. The half-life of Empagliflozin (Jardiance™) is 12.4 hours, thus the duration of safety follow-ups will be rounded up to be at least 72 hours (or 3 days).

The participant will be withdrawn from the study if they lose capacity and data collected up to that point will be used for analysis. As analysis will be on an intention-to-treat basis, there will be analysis of all data of participants receiving study medication (e.g. most safety analyses) and data will be admitted to the database even after the participant has withdrawn from the study.

Certain circumstances will necessitate the stopping or interruption of the study medication for a particular participant. Adverse event review and other safety/acceptability assessments will provide the information for the study clinician to withdraw or interrupt the study drug at any time during the trial. Specifically, it may be necessary to interrupt treatment with SGLT2-ingibitors (such as Empagliflozin (Jardiance™)) in participants who are hospitalised for major surgery or acute serious illness; treatment may be restarted once the participant's condition has stabilised and only once the necessary safety assessments have been performed. The decision to stop or interrupt and subsequently re-start the study treatment Empagliflozin (Jardiance™) will be documented in the participant's medical notes.

Any decisions regarding the withdrawal of participants from the study will be made by the study clinician and Principal Investigator.

Each participant will have a copy of the consent form and patient information leaflet placed in their hospital medical records. This will also include explicit notice of their in-study medication and a standard label will be used on the front of the medical notes to highlight to any reviewer that this individual is taking part in the study and any issue regarding contra-indication of a procedure or medication outside of the study should be discussed with a study clinician.

The standard label template is provided by the local trust and should contain the following information:

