7.2 Inclusion Criteria

- 1. Male and postmenopausal female participants aged between 30-75 years of age inclusive
- 2. Type 2 diabetes on diet and lifestyle control or stable dose of metformin only for at least 3 months
- 3. Stable weight (less than 5% change in body weight in last 3 months) determined by self-reporting or documentation in clinical records
- 4. HbA1c 42-86mmol/mol (6.0 10%)
- 5. eGFR≥60ml/min/1.73m²
- 6. BMI \geq 25kg/m²
- 7. Able and willing to give informed consent
- 8. Able to understand English

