7.3 Exclusion Criteria

- Females who are not postmenopausal (as menstrual cycle can affect appetite hormone concentrations)
 which is defined as "2 years post last menstrual period <50 years of age or 1 year post last menstrual
 period >50 years of age."
- 2. Type 2 diabetes on any other glucose lowering treatment except metformin
- 3. Patients with Type 1 diabetes
- 4. Patients on loop diuretics
- 5. Age <30 years and >75 years
- 6. BMI $< 25 \text{kg/m}^2$
- 7. Not able to give informed consent
- 8. Not able to understand English
- 9. Moderate to severe renal impairment (eGFR<60ml/min/1.73m²)
- 10. Unstable diabetes i.e. HbA1c >86mmol/mol (10%), recent hospital admission with diabetic emergency in last 3 months
- 11. Patients with familial renal glycosuria
- 12. Patients with recurrent balanitis, vaginal or urinary tract infections
- 13. Shift workers with rotating night/day shift patterns
- 14. Patients who have participated in another study of an investigational medicinal product in the last 3 months
- 15. Active malignancy
- 16. Serious illness with a life-expectancy of less than 1 year
- 17. Hypersensitivity to Empagliflozin (Jardiance™) or to any of the excipients
- 18. Patients with latent autoimmune diabetes in adults (LADA)

- 19. Patients with a history of chronic pancreatitis
- 20. Evidence of conditions that lead to restricted food intake or severe dehydration
- 21. Patients with a history of excessive alcohol consumption that in the opinion of the investigator or any sub-investigators would make implementation of the protocol or interpretation of the study results difficult or would preclude the safe participation of the subject in this protocol.
- 22. Patients on a severely calorie restricted diet (i.e., ≤800 calories per day)
- 23. Any contraindications to IMP

If the study clinician and/or Investigator deems it clinically inappropriate to include a potential participant in the study, that potential participant will deemed 'not eligible' and will not be enrolled/consented to the study (i.e., they will be classed as a screen failure and recorded as such on the visit CRF and in their medical notes). Clinicians will consider any emerging safety concerns throughout the duration of the study and subsequent eligibility of participants.

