11.2 The Number of Participants

The power calculation is based on the primary outcome of change in appetite hormones and a standard deviation of AUC of 96.2pg/ml of total PYY based on a study looking at the influence of resistance and aerobic exercise on hunger and circulating levels of total PYY in healthy males (Broom 2009). To detect a minimum clinically significant difference of 120pg/ml in AUC of total PYY between groups, we will require 15 participants in each of the four arms with 80% power and 2-sided alpha of 1.7%. This will allow three comparisons between arms. To account for up to 20% dropout, 19 participants will be required in each arm; therefore 76 participants will be recruited in total.

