11.7 Inclusion in Analysis

All analyses of outcome data will be carried out on a complete case basis according to randomised group. Therefore those with missing outcome data will be excluded from this analysis. As a sensitivity analysis, for the primary and main secondary outcome, multiple imputation will be used to perform an intention to treat analysis, and to assess the impact of missing outcome data. We will also conduct a per protocol analysis excluding those who report no longer taking their randomised treatment at the four follow ups.

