3.2 Analysis populations

3.2.1 Complete Case Population

All tests of the effect of treatment on outcomes will be conducted on a complete case (CC) population, using intention to treat principles. Patients will be excluded from analyses if they have missing data on any of the variables required for the analysis in question. Those with missing data at baseline will be included in the analysis using the missing indicator method. Detail is given in section 5.3.2. This population will be used for the main analysis of the primary outcome as well as all analyses of secondary outcomes.

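### Protocol 8.10 allows removal from the whole study for ineligibility found or arising after randomisation, with no week-24 PYY visit, so these people drop out of the complete-case primary analysis

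*Protocol*

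**What the plan says.** The heading of Protocol 8.10 refers to withdrawal from study treatment, but its text gives the investigator discretion to end participation in the study itself. One listed ground is "Ineligibility (either arising during the study or retrospective having been overlooked at screening"). No eligibility criterion is exempted. The only follow-up that 8.10 arranges is safety contact after an adverse-event withdrawal. The section also calls the analysis intention-to-treat and says that "data will be admitted to the database even after the participant has withdrawn from the study".

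Other relevant text:

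- Protocol 10.2 requires an end-of-study assessment only when an adverse event leads to stopping, and does not set it at week 24.
- Protocol 9.5 requires withdrawal of anyone who needs a medication that the exclusion criteria rule out.
- Protocol 7.3 says: "Clinicians will consider any emerging safety concerns throughout the duration of the study and subsequent eligibility of participants".
- Table 1 (Protocol 8.8) places the inclusion and exclusion check at visit 0 only.
- SAP 5.1 makes the primary outcome the change in time-averaged PYY AUC from baseline to week 24.
- SAP 3.2.1 says that tests of treatment effect "will be conducted on a complete case (CC) population, using intention to treat principles". Protocol 11.7 adds: "Therefore those with missing outcome data will be excluded from this analysis".
- On sample size, Protocol 11.2 says: "To account for up to 20% dropout, 19 participants will be required in each arm".

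**The concern.** Stopping a drug and ending follow-up are separate decisions, and 8.10 merges them. Once a participant is removed before visit 5, no week-24 PYY sample exists. Keeping the data already in the database does not create one. The person then leaves the primary estimate, although they were randomised and could often still attend.

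The two limbs of the ground differ. Ineligibility overlooked at screening is a baseline fact and does not depend on response, but removal for it is still an avoidable loss after randomisation. Ineligibility arising later could depend on treatment. BMI of at least 25 is an entry limit in both 7.2 and 7.3, and 7.2 requires "HbA1c 42-86mmol/mol". Empagliflozin and the diet act on weight, and the drug lowers HbA1c.

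The planned safeguards only partly help. Multiple imputation (SAP 5.4.3) is a sensitivity analysis, and its listed variables include no on-treatment weight or HbA1c. The postprandial GEE (SAP 5.4.2) needs at least one PYY value at week 24. The GEE across visits (SAP 5.3.3) keeps earlier PYY but is a secondary summary. At stake are completers in arms of 19 and, in principle, the balance between arms.

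**Working it through.** **1. The plan's own figure.** Inputs from Protocol 11.2: difference 120 pg/ml, SD 96.2, two-sided alpha 0.017, power 80%. With the two-sample noncentral t, noncentrality = 120 / (96.2 × √(1/n₁ + 1/n₂)) and df = n₁ + n₂ − 2. Power is 76.8% at 14 per arm and 80.3% at 15, so 15 is reproduced. Dropout: 15 / 0.8 = 18.75, rounded up to 19; 4 × 19 = 76. Standard error at 15 v 15: 96.2 × √(2/15) = 35.1 pg/ml.

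**2. Power cost of one lost completer in one arm** (same formula):

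| Starting point | Power | After losing one | Power |
|---|---|---|---|
| 19 v 19 | 90.4% | 18 v 19 | 89.4% |
| 17 v 17 | 86.1% | 16 v 17 | 84.8% |
| 15 v 15 | 80.3% | 14 v 15 | 78.6% |

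The loss is 1.0, 1.3 and 1.7 points. A loss in the placebo-only arm affects all three contrasts, because that arm is the shared reference.

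**3. How many could meet the BMI or HbA1c ground.** The documents give no baseline distributions, so this step is a simulation on assumptions. The event is BMI below 25 or HbA1c outside 42-86 mmol/mol at week 2, 6 or 12.

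- Drug effect: −1.8 kg and 0.66% × 10.93 ≈ 7 mmol/mol (Protocol section 4).
- Assumed effect of drug plus diet: −5 kg and −9 mmol/mol.
- Assumed base case: BMI mean 32, SD 4.5, cut at 25; HbA1c mean 57, SD 9, within-person SD 2; SD of weight change 2.5 kg; height 1.70 m; share of effect reached at weeks 2/6/12 of 30/60/85% (weight) and 20/55/85% (HbA1c).
- Low case: BMI mean 33, HbA1c mean 65, SD 8, within-person SD 1.5, SD of weight change 1.5 kg.
- High case: BMI mean 31, HbA1c mean 55, within-person SD 2.5, SD of weight change 3.5 kg.

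| Case | No effect | Drug | Drug plus diet |
|---|---|---|---|
| Low | 0.8% | 2.9% | 6.5% |
| Base | 3.7% | 14.6% | 22.3% |
| High | 6.9% | 20.7% | 29.7% |

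Most of the drug-arm crossings are on HbA1c. BMI alone, in the base case, gives 0.9%, 2.1% and 5.6%. Per 19 participants that is 19 × 0.021 = 0.4 on drug and 19 × 0.056 = 1.1 on drug plus diet. These are people who cross a limit, not people removed. The documents give no removal rate, and zero is possible.

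**4. Bias between arms.** Suppose every crosser is removed and PYY change correlates 0.5 with weight change (assumed). The mean PYY of those remaining shifts in the placebo arm as well, so the relevant quantity is the active-arm shift minus the placebo shift.

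| Case | Drug v placebo | Drug plus diet v placebo |
|---|---|---|
| Base | 0.4 pg/ml | 0.9 pg/ml |
| High | 0.7 pg/ml | 1.8 pg/ml |

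A weaker correlation or partial removal gives less. The largest value is 1.8 / 35.1 = 5% of a standard error and 1.8 / 120 = 1.5% of the target difference. The diet-only arm was not simulated.

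**The case against.** The strongest reply is that the treatment-related route is read into the text. Removal is discretionary, Table 1 checks criteria once, and 7.3 links later eligibility to safety. An HbA1c below 42 fails an inclusion limit but is not an exclusion criterion. Weight change is an endpoint and two arms are prescribed a diet, so removing people for losing weight would defeat the trial. A reader might infer from 8.10 that responders are to be taken out and the drug contrast thereby distorted. The documents do not support that: nothing directs withdrawal for a low BMI or HbA1c, and even full removal gives the negligible bias shown in the working. What stands is that 8.10 does not rule such removal out.

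Second, investigator withdrawals are a form of dropout and 20% is already allowed. That largely stands: 15 v 19 still gives 85.6%. Power falls below 80% only if other losses have already used the allowance.

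Third, the missing follow-up is common to the whole 8.10 list, including intolerance, where withdrawal is mandatory. That is true, and those grounds are not sized here. It does not excuse this one, where attendance at visit 5 would usually remain possible.

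Fourth, week-24 PYY measured off drug or on other glucose-lowering therapy would dilute the drug effect in a mechanistic trial. That stands as a cost of the fix.

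**Conclusion.** The point holds as a minor one. Following 8.10 as written loses randomised participants from the primary analysis for a reason that does not require it, against the plan's stated intention-to-treat aim. SAP 3.2.3 already lets substantial deviations leave the per-protocol set, so removal from the study serves no analytic purpose.

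The size is about 1 to 2 points of power per lost completer for one contrast, partly absorbed by the dropout allowance. The number affected is unknown and may be near zero. Between-arm bias is negligible, under about 2 pg/ml, on assumed distributions and an assumed correlation of at most 0.5. A reader might infer that the trial is underpowered or the primary comparison materially biased; neither follows. The absence of a week-24 visit rests on no section providing one, not on a prohibition. The power figures rest only on the plan's own inputs; the crossing shares and bias rest on assumptions that the documents neither confirm nor contradict.

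**What to change.** - **Protocol 8.10:** state that the BMI, HbA1c and weight-stability limits apply at entry only. State that ineligibility found or arising after randomisation may stop study drug but does not by itself end follow-up. Ask such participants, if they consent, to attend the planned visit 5.
- **Protocol 9.5:** amend so that needing a prohibited medication stops study drug rather than follow-up. Without this change the two sections would conflict.
- **SAP 3.2.1:** add one sentence saying that these participants are analysed in their randomised group. The per-protocol set may still exclude them.

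The investigator's safety discretion is unchanged. Extending the same rule to intolerance would also mean changing Protocol 9.1.

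The cost is a few sentences in one protocol amendment and one in the SAP, with no extra participants and no visit beyond those planned. The downside is that a few week-24 values will come from people outside the entry range, off drug or on other therapy, which slightly dilutes the drug contrast. The per-protocol analysis covers this.

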8.11 Source Data

Source documents are original documents, data, and records from which participants' CRF data will be obtained. These include, but are not limited to, hospital records (from which medical history and previous and concurrent medication will be summarised into the CRF), clinical and office charts, laboratory and pharmacy records, diaries, microfiches, radiographs, and correspondence.

CRF entries will be considered source data if the CRF is the site of the original recording (e.g., there is no other written or electronic record of data). All documents will be stored safely in a secure office environment and will be listed on a source data agreement. On all study-specific documents, other than the signed consent, the participant will be referred to by the study participant number/code only, and not by name.

9. TREATMENT OF TRIAL PARTICIPANTS

9.1 Description of Study Treatment & Pharmacy Process

The study medication is Empagliflozin (Jardiance[™]) which is an oral film-coated tablet manufactured by Boehringer Ingelheim pharmaceutical company. Placebo will also be manufactured and supplied by Boehringer Ingelheim. Both Empagliflozin (Jardiance[™]) and the placebo can be described as follows: pale yellow, biconvex film-coated tablets, one side debossed with the Boehringer Ingelheim company symbol and the other side debossed with "S25". The dosage will be 25mg once daily for Empagliflozin (Jardiance[™]), which is the maximum dose, licensed for the treatment of Type 2 Diabetes in the UK. The placebo will be labelled as '25mg once daily' to match. There is a lower dose of Empagliflozin (Jardiance[™]) 10mg daily. However, this dose will not be used in the study and participants who do not tolerate Empagliflozin (Jardiance[™]) 25mg daily will be discontinued from the study.

The ingredients of the placebo are:

- > Tablet core
- Lactose monohydrate
- Microcrystalline cellulose
- Hydroxypropylcellulose
- Croscarmellose sodium
- Colloidal anhydrous silica
- Magnesium stearate
- > Film coating
- Hypromellose
- Titanium dioxide (E171)
- Talc
- Macrogol (400)
- Iron oxide yellow (E172)

The licensed product Empagliflozin (Jardiance™) will be handled according to UHL pharmacy in-house protocols. Specifically, the employment, dosing, handling, storage and destruction of Empagliflozin (Jardiance™) and its placebo will be conducted in accordance with the specified conditions of its approved labelling and in line with our UHL pharmacy guidelines. All study medication dosage will not exceed the stated recommendations of local guidelines and the British National Formulary. All contra-indications will be checked as part of the eligibility criteria.

Boehringer Ingelheim will supply both Empagliflozin (Jardiance™) and the placebo to the third party company ALMAC who will arrange the packaging, blinding and labelling of both Empagliflozin (Jardiance™) and the placebo prior to delivery and storage of the finished blinded stock to Leicester General Hospital Pharmacy.

Study medication may be suspended or stopped by the study team if they become aware of the participant undergoing any contra-indicated procedure for out of study clinical care. This will be documented in the individual's study and medical notes and decision on any potential withdrawal from the study on this basis will reside with the PI. Recommencing of the study drug will follow individual safety assessments in-line with the procedure in question.

Prior to starting treatment with empagliflozin, the following factors will be considered as they may predispose patients to acute kidney injury:-

- decreased blood volume
- chronic kidney insufficiency
- congestive heart failure
- on diuretics, ACE inhibitors, ARBs, and NSAIDs

Kidney function will be assessed prior to starting treatment with empagliflozin and at each study visit. If acute kidney injury occurs, empagliflozin will be promptly discontinued and kidney impairment treated using standard guidelines.

9.2 Storage of Study Treatment

The study medication Empagliflozin (Jardiance™) and placebo will be stored at room temperature in a designated, restricted, clinical trials area within the pharmacy department at Leicester General Hospital. ALMAC will manage drug distribution with 50% of the drugs required (plus 10-20% for waste) being provided in the first instance. Thereafter the drugs will be automatically ordered and distributed to the Pharmacy as this is part of the functionality available on the randomization system.

9.3 Compliance with Study Treatment

The participants will be instructed to return all unused or part-used medication and packaging from used medication at each visit. The Investigator may withdraw the participants if they consider dose compliance is unsatisfactory.

9.4 Accountability of the Study Treatment

The study medication will be supplied by Boehringer Ingelheim to Leicester General Hospital pharmacy. All movements of study medication between Boehringer Ingelheim and pharmacy will be documented.

The Investigator will use a trial specific prescription form and a member of the Investigator team will collect the medication Empagliflozin (Jardiance™) or placebo.

The participant will be asked to bring all unused medication and packaging back to the clinic at each visit where it will be returned to pharmacy and the clinical trial pharmacists will be responsible for destroying the returned stock.

9.5 Concomitant Medication

Throughout the study, Investigators will be able to prescribe any concomitant medications or treatments

deemed necessary to provide adequate supportive care except for those listed in the exclusion criteria. If these are required, the participant will be withdrawn.

Any medication, other than the study medication taken during the study will be recorded in the CRF.

Contraindicated medications during the study will include any other glucose-lowering therapies apart from metformin. Loop diuretic therapy will also be contraindicated.

As study drug Empagliflozin (Jardiance™), placebo and metformin do not cause hypoglycaemia, participants will not be expected to perform home blood glucose monitoring during the study.

10. SAFETY REPORTING

10.1 Definitions

Adverse Event (AE)

An AE or adverse experience is:

Any untoward medical occurrence in a patient or clinical investigation participants administered a medicinal product, which does not necessarily have to have a causal relationship with this treatment (the study medication).

An AE can therefore be any unfavourable and unintended sign (including an abnormal laboratory finding), symptom or disease temporally associated with the use of the study medication, whether or not considered related to the study medication.

Adverse Reaction (AR)

All untoward and unintended responses to a medicinal product related to any dose. The phrase "responses to a medicinal product" means that a causal relationship between a study medication and an AE is at least a reasonable possibility, i.e., the relationship cannot be ruled out.

All cases judged by either the reporting medically qualified professional or the Sponsor as having a reasonable suspected causal relationship to the study medication qualify as adverse reactions.

Severe Adverse Events (SAE)

To ensure no confusion or misunderstanding of the difference between the terms "serious" and "severe", which are not synonymous, the following note of clarification is provided:

The term "severe" is often used to describe the intensity (severity) of a specific event (as in mild, moderate, or severe myocardial infarction); the event itself, however, may be of relatively minor medical significance (such as severe headache). This is not the same as "serious," which is based on patient/event outcome or action criteria usually associated with events that pose a threat to a participant's life or functioning. Seriousness (not severity) serves as a guide for defining regulatory reporting obligations.

Serious Adverse Event or Serious Adverse Reaction (SAE or SAR)

A serious adverse event or reaction is any untoward medical occurrence that at any dose:

- Results in death,
- Is life-threatening,

NOTE: The term "life-threatening" in the definition of "serious" refers to an event in which the participant was at risk of death at the time of the event; it does not refer to an event which hypothetically might have caused death if it were more severe.

- Requires inpatient hospitalisation or prolongation of existing hospitalisation,
- Results in persistent or significant disability/incapacity, or
- Is a congenital anomaly/birth defect.
- Other important medical events*

*Other events that may not result in death, are not life threatening, or do not require hospitalisation, may be considered a serious adverse event when, based upon appropriate medical judgement, the event may jeopardise the patient and may require medical or surgical intervention to prevent one of the outcomes listed above.

Expected Serious Adverse Events/Reactions (SAE)

The most common adverse events associated with Empagliflozin (Jardiance™) are urinary tract and mycotic fungal infections (e.g. balanitis) and volume depletion leading to dehydration, postural hypotension and dizziness. If these events lead to hospitalisation of the participant, they will require immediate reporting to the study team. Otherwise, they will be treated as an AE and need reporting to the study team within 2 working days.

Abnormalities of renal and liver function will also be closely monitored as part of the usual study visits and any significant clinical deterioration in renal and/or liver function will be reported as an SAE. A serious deterioration in renal function to be classified as an SAE will be a reduction in eGFR to less than 30ml/min/1.73m². A serious deterioration in liver function will be classified as an SAE if ALT or AST is 3x greater than the upper limit of normal (ULN).

Ketoacidosis and Diabetic Ketoacidosis (DKA) have recently been reported as a possible serious SAE occurring with SGLT-2 inhibitor use by the US Food and Drugs Administration. Participants will be closely monitored for the development of this SAE and will be advised to seek medical attention immediately if they experience symptoms such as difficulty breathing, nausea, vomiting, abdominal pain, confusion, unusual fatigue or sleepiness, anorexia, excessive thirst, dehydration, low food intake, weight loss, infection, poor control of diabetes, and/or only moderately increased glucose levels.

In patients where DKA is suspected or diagnosed, treatment with SGLT-2 inhibitors will be discontinued immediately. Restarting SGLT-2 inhibitor treatment in patients with previous DKA while on SGLT-2 inhibitor treatment is not recommended unless another clear precipitating factor is identified and resolved. Treatment will also be interrupted in patients who are hospitalised for major surgical procedures or acute medical illnesses. In both cases, treatment with SGLT-2 inhibitors may be restarted once the patient's condition has stabilised and only once the necessary safety assessments have been performed. The decision to stop or interrupt and subsequently re-start the study treatment Empagliflozin (Jardiance™) will be documented in the participant's medical notes. Any decisions regarding the withdrawal of participants from the study will be made by the study clinician and Principal Investigator. Further details about the discontinuation/withdrawal from, or interruption of, the study treatment can be found in Section 8.9, above (pg. 30).

Suspected Unexpected Serious Adverse Reactions (SUSAR)

A serious adverse reaction, the nature or severity of which is not consistent with the Summary of Product Characteristics for Empagliflozin (Jardiance™) will be reported as a SUSAR.

Adverse Events of Special Interests (AESI)

- Decreased renal function: creatinine value shows a ≥ 2 fold increase from baseline and is above ULN
- Hepatic injury defined by the following alterations of liver parameters after randomization at visit 1:-
 - Elevation of AST and/or ALT≥3 fold ULN combined with an elevation of total bilirubin≥2 fold ULN measured in the same blood draw sample
 - o Isolated elevation of AST and/or ALT≥5 fold ULN irrespective of any bilirubin elevation
- Diabetic Ketoacidosis (DKA)
 - O DKA is defined by the diagnostic criteria in the table below, and as defined by the American Diabetes Association (ADA).

Investigators should note that not all criteria in Table 2 (below) need to apply for the diagnosis of DKA, and clinical judgment should also be taken into consideration. Due to its mechanism of action, Empagliflozin (Jardiance™) may potentially modify the clinical presentation of DKA which may occur at lower plasma glucose levels than stated in the table below.

- Events involving Lower Limb Amputation
 - This definition includes amputation (i.e. resection of a limb through a bone), disarticulation (i.e. resection of a limb through a joint) and auto-amputations (i.e. spontaneous separation of non-viable portion of the lower limb).
 - Not included in this definition are debridement (removal of callus or dead tissue), procedures
 on a stump (like stump revision, drainage of an abscess, wound revision etc.) and other
 procedures (e.g., nail resection or removal) without a concomitant resection of a limb
 (amputation or disarticulation).
 - Each lower limb amputation, disarticulation, or auto-amputation should be reported separately. The SAE report should include the date of the procedure, the level of amputation or disarticulation, the medical condition(s) leading to the procedure and if the patient had some of the known risk factor(s) for lower limb amputation.

If any AESIs occur they will be reported to the Sponsor and Boehringer Ingelheim using the same procedure as reporting Serious Adverse Events (SAEs; see Section 10.3, pg. 38).

Table 2 - Diagnostic criteria for DKA

	DKA		
	Mild	Moderate	Severe
Plasma glucose (mg/dL)	>250	>250	>250
Arterial pH	7.25-7.30	7.00-7.24	<7.00
Serum bicarbonate (mEq/L)	15-18	10 to <15	<10
Urine ketones*	Positive	Positive	Positive
Serum ketones*	Positive	Positive	Positive
Effective serum osmolality (mOsm/kg)**	Variable	Variable	Variable
Anion gap***	>10	>12	>12
Alteration in sensoria or mental obtundation	Alert	Alert/drowsy	Stupor/coma

Nitroprusside reaction method

** Calculation: 2[measured Na (mEq/L) + glucose (mg/dL)/18

*** Calculation: (Na+) - (Cl- + HCO3-) (mEq/L)

